8.5.5 Change from baseline for other clinical efficacy endpoints

Change from baseline to each scheduled assessment for the following endpoints will be analyzed: acne measured with total lesion count and investigator global assessment of acne, hirsutism measured with Ferriman–Gallwey (FG) score, metabolic features (Hb A1c, fasting insulin/glucose, body mass index (BMI), lipids [LDL cholesterol, HDL cholesterol, total cholesterol, triglycerides], waist circumference), ovarian volume, and endpoints related to subject's quality of life (PCOSQ [emotions, body hair, weight, infertility problems, and menstrual problems], and MBQ). The analysis will be based on

one-way ANCOVA with treatment group as the main effect, and baseline FG score (< 8 , ≥ 8), baseline normal/obese status ($\text{BMI} < 30$, ≥ 30), and baseline value of the corresponding endpoint being analyzed as the covariates.

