8.2 Handling of Missing Data

Missing data will be imputed using the following methods for the efficacy analyses:

Mixed-Effect Model Repeat Measurement (MMRM): The repeated measures analyses will be conducted using mixed models including observed measurements at all visits. The mixed model includes the categorical fixed effects of treatment, visit and treatment-by-visit interaction, subject as a random effect, and the continuous fixed covariates of baseline measurement. An unstructured variance covariance matrix will be used. Parameter estimation is based on the assumption of data being missing at random and using the method of restrictive maximum likelihood (REML). Missing data will not be imputed for MMRM analysis.

Observed Cases (OC): The OC analysis will not impute values for missing evaluations, and thus a subject who does not have an evaluation on a scheduled visit will be excluded from the OC analysis for that visit. OC will exclude values after a subject prematurely discontinues from study drug.

Multiple Imputation (MI): The MI approach will be used as a sensitivity analysis for the primary endpoint. For the primary endpoint, 20 'complete' datasets will be generated using SAS PROC MI. The seed will be 123. Using the Cochran-Mantel-Haenszel (CMH) model adjusted for FG score ($< 8, \geq 8$) and normal/obese status ($BMI < 30, \geq 30$) at Baseline, the imputed endpoints will be analyzed using each of the 20 datasets. SAS PROC MIANALYZE will be used to generate the final inferences of difference of proportion of menstrual cycle responders between each elagolix group and placebo.

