8.4 Secondary Efficacy Analyses

The key secondary endpoint is change from baseline in the area under the luteinizing hormone (LH) serum concentration-time curve over the 4 hours (area under the curve [AUC]) at Day 7. Serial blood samples for LH assay will be collected at Baseline and Weeks 1, 4, and 16 according to the following schedule: 0 hour, 0.5, 1, 1.5, 5, 2.5, 3, 3.5, and 4 hours. The AUC over the 4 hours will be calculated based on the linear trapezoidal rule.

The analysis for the key secondary endpoint will be based on a mixed-effects model with repeated measures (MMRM). If appropriate, the natural logarithmic transformation or other transformation may be employed for LH AUC. The MMRM analysis will include the fixed categorical effects of treatment, visit, treatment-by-visit interaction, baseline FG score ($< 8, \geq 8$), and baseline normal/obese status ($\text{BMI} < 30, \geq 30$), subject as a random effect, and the continuous fixed covariate of baseline LH AUC. Each elagolix dose group will be compared to the placebo group; the LS mean of treatment difference and associated 90% CI and p-value will be reported.

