8.5.2 LH, FSH, testosterone and other hormones

The changes from baseline to each scheduled assessment of the hormone parameters will be analyzed using a mixed-effects model with repeated measures (MMRM). If appropriate, the natural logarithmic transformation or other transformation may be employed for the hormone parameters. The MMRM analysis will include the fixed categorical effects of treatment, visit, treatment-by-visit interaction, baseline FG score ($< 8, \geq 8$), and baseline normal/obese status ($\text{BMI} < 30, \geq 30$), subject as a random effect, and the continuous fixed covariate of baseline hormone value.

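### SAP 8.5.5 analyses repeatedly measured endpoints by a separate ANCOVA at each visit with no missing-data rule, so later-visit differences can be biased if stopping depends on response and differs between arms

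*SAP*

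**What the plan says.** SAP 8.5.5 opens with "Change from baseline to each scheduled assessment for the following endpoints will be analyzed" and then lists total acne lesion count, IGA, FG score, metabolic features, ovarian volume, the PCOSQ domains and the MBQ. The method is "one-way ANCOVA with treatment group as the main effect, and baseline FG score", with BMI stratum and the endpoint's own baseline value as further covariates. That is one cross-sectional model per visit. The section has no visit term and no missing-data rule.

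SAP 8.2 defines three approaches:

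- **MMRM:** "The repeated measures analyses will be conducted using mixed models including observed measurements at all visits", and "Parameter estimation is based on the assumption of data being missing at random". SAP 8.4 assigns it to LH AUC and 8.5.2 to the hormones. Both add the FG and BMI strata, which the 8.2 description lacks.
- **Observed cases (OC):** "a subject who does not have an evaluation on a scheduled visit will be excluded from the OC analysis for that visit", and "OC will exclude values after a subject prematurely discontinues from study drug".
- **Multiple imputation:** a sensitivity analysis for the primary endpoint.

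Protocol 5.6 asks that women who stop study drug stay in the regular visits unless they withdraw consent. SAP 10.0 states that type I error is not controlled for any analysis.

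**The concern.** Every 8.5.5 endpoint is measured at two or more visits after Baseline (protocol Appendix D; Operations Manual 2.2). A woman who leaves after Week 8 has values that carry information about her missing Week 24 value. The visit-wise ANCOVA does not use them; an MMRM does. The SAP gives no reason for treating these endpoints differently from the hormones. Fasting insulin, for example, is drawn at the same visits as androstenedione and AMH, yet is listed in 8.5.5.

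These endpoints bear on the clinical hypothesis of improved hyperandrogenic symptoms (protocol 2.1) and on the rationale for the upper dose range (protocol 4.2). Groups have 20 or 30 women, and the sample-size text gives no allowance for dropout. The SAP is version 1.0 of 29 October 2019. The protocol synopsis is dated 02 October 2020, and that version lets missed FG, acne, weight and waist assessments wait for the next on-site visit. Gaps at single visits are therefore also likely.

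**Working it through.** **1. Is there a figure in the plan to reproduce?** Not for these endpoints: no effect size, SD, correlation or dropout rate is given. The only power figure, at least 85% for the primary endpoint, is met and does not bear on this point. With 10% of 30 against 50% of 20 and two-sided alpha 0.05, the pooled SE is √(0.26 × 0.74 × (1/30 + 1/20)) = 0.1266 and the unpooled SE is √(0.09/30 + 0.25/20) = 0.1245. Then (0.40 − 1.96 × 0.1266)/0.1245 = 1.22, or about 88.9%.

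**2. Is an MMRM feasible?** Post-baseline visits by endpoint:

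| Endpoint | Weeks |
|---|---|
| HbA1c | 12, 24 |
| FG, PCOSQ, MBQ | 8, 16, 24 |
| Acne count, IGA, BMI, waist, lipids, glucose, ovarian volume | 4, 8, 16, 24 |
| Fasting insulin | 4, 8, 12, 16, 24 |

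It is feasible for all of them.

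**3. Which missing-data rule applies?** MMRM is assigned to 8.4 and 8.5.2, and multiple imputation to the primary endpoint. Observed cases is what remains for 8.5.5. This is an inference, because 8.5.5 does not say so.

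**4. Size by hand.** Assume correlation 0.7 between any two visits, Baseline included, in SD units. Given baseline:

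- residual variance = 1 − 0.7² = 0.51, so residual SD = 0.714
- covariance of two visits' residuals = 0.7 − 0.49 = 0.21, so the slope of Week 24 on an earlier visit = 0.21/0.51 = 0.412

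Suppose the 30% of placebo women with the worst residuals at one earlier visit all leave, and elagolix women leave at random. The mean of the remaining placebo women at that visit shifts by φ(0.524)/0.70 × 0.714 = 0.348/0.70 × 0.714 = 0.355 SD. Their Week 24 mean shifts by 0.355 × 0.412 = 0.146 SD, and the treatment difference is too small by that amount. Softer selection gives less. The same rule and rate in both arms makes the two shifts nearly cancel. Selection only in the elagolix arm reverses the sign.

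**5. Size by simulation.** Documented input: 30 + 5 × 20 women. Assumed: visits at Weeks 4, 8, 16 and 24, true Week 24 effect 0.50 SD, correlation 0.5, 0.7 or 0.85, and dropout without return after Week 4. There were 4000 trials per setting (2000 with no dropout). Week 24 observed-case ANCOVA was compared with an unstructured MMRM, with FG and BMI strata left out of both. Ranges are over the three correlations; Monte Carlo error of the bias is about 0.003 to 0.005 SD.

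| Stopping pattern | Missing | ANCOVA bias (SD) | Variance ratio ANCOVA/MMRM |
|---|---|---|---|
| None | 0% | 0.000 to +0.004 | 1.00 |
| Completely random | 20–30% | −0.005 to +0.010 | 1.04–1.10 |
| Response-related, same rule and rate | 20–30% | −0.012 to +0.003 | 1.01–1.06 |
| Response-related, placebo 30%, elagolix 10% | as stated | −0.075 to −0.056 | 1.02–1.03 |
| Response-related, placebo 10%, elagolix 30% | as stated | +0.044 to +0.063 | 1.00–1.03 |
| Only placebo response-related | 20% | −0.066 to −0.060 | 1.04–1.06 |
| Response-related in opposite directions | 20–30% | −0.231 to −0.123 | 0.99–1.03 |

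MMRM bias was at most 0.011 SD in every row. Further runs of the only-placebo pattern, with correlation about 0.7 and about 22 to 33% missing, gave ANCOVA shortfalls from 0.04 SD (weak selection) to 0.13 SD (strong selection). That is 0.04/0.50 = 8% to 0.13/0.50 = 26% of the assumed effect.

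**6. Precision.** A variance ratio of 1.10 is √1.10 = 1.05 in SE, so at most about 5%. With complete data the two methods give the same estimate. At the first post-baseline visit, when women who leave do not return, they give essentially the same one.

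**The case against.** The strongest reply is that the bias is conditional and the documents give no dropout rate or pattern from which to predict it. That stands. A reader might infer that the ANCOVA is biased as it stands and understates the drug effect. The documents do not support this: material bias needs stopping that depends on response and also differs between arms, and the direction can reverse. Nor should a shortfall of about a quarter, the strong-selection end, be read as the expected error.

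A reader might also infer a clear gain in power. The variance gain is small and sometimes nil; any large power difference in such simulations comes mainly from removing the assumed bias.

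It is fair, too, that 8.5.5 never mentions observed cases. Sections 8.5.3 and 8.5.4 exclude women who discontinue from their main count analyses in so many words; 8.5.5 is silent. With the full analysis set and the follow-up in protocol 5.6, values after stopping drug might be meant to count. This limits how firmly one can say which women are lost, but the silence is itself part of the problem.

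Nor do the hyperandrogenism conclusions rest on 8.5.5 alone: the patient global impressions of acne and hirsutism are compared by logistic regression in 8.5.6.

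Finally, MMRM protects only under missing at random, and it does not address the scale of the 0-to-5 IGA or of lesion counts. Both points stand; the second applies equally to the ANCOVA.

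**Conclusion.** The point holds in conditional form. SAP 8.5.5 uses a separate ANCOVA at each visit for endpoints with two to five post-baseline visits and states no missing-data rule, while the SAP uses a repeated-measures model for comparable hormone data. If stopping depends on response and differs between arms, the Week 24 difference can be wrong in either direction. With a true effect of 0.50 SD, correlation about 0.7, about 30% missing and only placebo stopping related to response, it is about 0.04 to 0.13 SD too small. It reaches 0.12 to 0.23 SD if selection runs in opposite directions in the two arms. With no dropout or completely random dropout there is essentially no bias, and with a common mechanism and rate it is about 0.01 SD.

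Effect size, correlation, dropout rates and stopping rules are all assumptions; intermittent gaps were not simulated. Severity is minor to moderate: these are additional endpoints in a proof-of-concept study without type I error control.

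**What to change.** In SAP 8.5.5:

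1. For every endpoint with two or more post-baseline visits, use the MMRM of 8.5.2: treatment, visit, treatment-by-visit, baseline value, and FG and BMI strata. Report the difference from placebo with its 90% CI at each visit.
2. State whether values collected after stopping study drug, which protocol 5.6 asks for, are included. The 8.2 MMRM text does not say, and the answer decides whether the estimate describes the effect while on drug or regardless of stopping.
3. Keep the visit-wise ANCOVA as supportive, and name its missing-data rule. If the ANCOVA stays as the main analysis, it still needs that rule.

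Because the sponsor is unblinded throughout (protocol 7.1), date the change and give its reason.

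The cost is SAP wording and a little more programming, since the model is already needed for 8.5.2. No new data are required. The downside is reliance on missing at random.

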8.5.6 Patient Global Impression (PGI) for Acne and Hirsutism

For patient global impression for acne and hirsutism (PGIA and PGIH), the number and percentage of subjects in each response category will be summarized at each scheduled assessment during the Treatment Period. No statistical test will be performed.

For PGIA and PGIH, the response categories of "Much better" and "A little better" will be combined together. The remaining four categories will be combined and labeled "Otherwise." The number and percentage of subjects with response of (a) "Much better" or "A little better," and (b) "Otherwise" will be summarized at each scheduled assessment during the Treatment Period. Comparisons between each elagolix group and placebo will be made using a logistic regression model with (a) "Much better" or "A little better"/(b) "Otherwise" as the dependent variable, treatment as the main effect, and baseline FG score (< 8 , ≥ 8) and baseline normal/obese status ($\text{BMI} < 30$, ≥ 30) as the covariates.

9.0 Safety Analyses

9.1 General Considerations

Safety analyses will be carried out using Safety Analysis Set. All safety analyses will be based on observed data. Unless otherwise specified, missing data will not be imputed.

For continuous variables, when the analyses of change and/or percent change from Baseline to post-baseline visit(s) are performed, the within-group change from Baseline to each relevant visit will be summarized by treatment group with the mean, SE, and 95% CIs. The between-group differences will be summarized with the mean, SE, 95% CIs, and P value when applicable. P value will be compared to an alpha level of 0.05. At each post-baseline visit, the Baseline mean and post-baseline visit mean will be calculated for all subjects with baseline and post-baseline value at that visit by treatment group.

Categorical data will be summarized by number and percentage of subjects by treatment group.

9.2 Adverse Events

Adverse events (AEs) will be summarized and presented using primary MedDRA System Organ Classes (SOCs) and preferred terms (PTs) according to the version of the MedDRA coding dictionary used for the study at the time of database lock. The actual version of the MedDRA coding dictionary used will be noted in the AE tables and in the clinical study report. Specific adverse events will be counted once for each subject for calculating percentages, unless stated otherwise. In addition, if the same adverse event occurs multiple times within a subject, the highest severity and level of relationship to investigational product will be reported.

9.2.1 Treatment-Emergent Adverse Events

Treatment-emergent AEs are defined as any AE with the onset that is after the first dose of study drug. Events where the onset date is the same as the study drug start date are assumed to be treatment-emergent. All treatment-emergent AEs will be summarized overall, as well as by primary MedDRA SOC and Preferred Term. The SOCs will be presented in alphabetical order, and the PTs will be presented in alphabetical order within each SOC.

The number and percentage of subjects experiencing treatment-emergent AEs will be summarized.

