## 5.6 Follow-Up for Subject Withdrawal from Study

To minimize missing data for efficacy and safety assessments, subjects who prematurely discontinue study drug treatment should continue to be followed for all regularly scheduled visits, unless subjects have decided to discontinue the study participation entirely (withdrawal of informed consent). Subjects should be advised on the continued scientific importance of their data even if they discontinue treatment with study drug early.

If a subject prematurely discontinues study participation (withdrawal of informed consent), the procedures outlined for the Premature Discontinuation visit (PD visit) should be completed as soon as possible, preferably within 2 weeks. In addition, if subject is willing, a 30-day follow-up phone call after the last dose of study drug may be completed to ensure all treatment-emergent AEs/serious adverse events (SAEs) have been resolved.

All attempts must be made to determine the date of the last study drug dose and the reason for discontinuation of study drug or study participation. The information will be recorded on the appropriate eCRF page. However, these procedures should not interfere with the initiation of any new treatments or therapeutic modalities that the investigator considers necessary to treat the subject's condition. Following discontinuation of study drug, the subject will be treated in accordance with the investigator's best clinical judgment, irrespective of whether or not the subject decides to continue participation in the study.

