#### Medical Complaints/Adverse Events and Serious Adverse Events

An AE is defined as any untoward medical occurrence in a subject or clinical investigation subject administered a pharmaceutical product and which does not necessarily have a causal relationship with this treatment. An AE can therefore be any unfavorable and unintended sign (including an abnormal laboratory finding), symptom, or disease temporally associated with the use of a medicinal (investigational) product, whether or not the event is considered causally related to the use of the product.

The investigators will monitor each subject for clinical and laboratory evidence of AEs on a routine basis throughout the study. All AEs will be followed to a satisfactory conclusion.

An AE can result from use of the drug as stipulated in the protocol or approved labeling, as well as from accidental or intentional overdose, drug abuse, or drug withdrawal. Any worsening of a pre-existing condition or illness is considered an AE. Worsening in severity of a reported AE should be reported as a new AE. Laboratory abnormalities and changes in vital signs are considered to be AEs only if they result in discontinuation from the study, necessitate therapeutic medical intervention, and/or if the investigator considers them to be AEs.

An elective surgery/procedure scheduled to occur during a study will not be considered an AE if the surgery/procedure is being performed for a pre-existing condition and the surgery/procedure has been pre planned prior to study entry. However, if the pre-existing condition deteriorates unexpectedly

during the study (e.g., surgery performed earlier than planned), then the deterioration of the condition for which the elective surgery/procedure is being done will be considered an AE.

If an AE, whether associated with study drug or not, meets any of the following criteria, it is to be reported to AbbVie clinical pharmacovigilance or contract research organization (CRO) (as appropriate) as an SAE within 24 hours of the site's being made aware of the SAE (refer to Section 4.3 of the Operations Manual for reporting details and contact information):

Death of Subject	An event that results in the death of a subject.
Death of Subject	

**Life-Threatening** An event that, in the opinion of the investigator, would have

resulted in immediate fatality if medical intervention had not been taken. This does not include an event that would have been fatal if it

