had occurred in a more severe form.

Hospitalization or Prolongation of Hospitalization An event that results in an admission to the hospital for any length of time or prolongs the subject's hospital stay. This does not include an emergency room visit or admission to an outpatient facility.

**Congenital Anomaly** An anomaly detected at or after birth, or any anomaly that results in

fetal loss.

Persistent or Significant Disability/Incapacity

An event that results in a condition that substantially interferes with the activities of daily living of a study subject. Disability is not intended to include experiences of relatively minor medical significance such as headache, nausea, vomiting, diarrhea, influenza, and accidental trauma (e.g., sprained ankle).

Important Medical Event Requiring Medical or Surgical Intervention to Prevent Serious Outcome An important medical event that may not be immediately lifethreatening or result in death or hospitalization, but based on medical judgment may jeopardize the subject and may require medical or surgical intervention to prevent any of the outcomes listed above (i.e., death of subject, life threatening, hospitalization, prolongation of hospitalization, congenital anomaly, or persistent or significant disability/incapacity). Additionally, any elective or spontaneous abortion or stillbirth is considered an important medical event. Examples of such events include allergic bronchospasm requiring intensive treatment in an emergency room or at home, blood dyscrasias or convulsions that do not result in inpatient hospitalization, or the development of drug dependency or

All AEs reported from the time of study drug administration until 30 days after discontinuation of study drug administration will be collected, whether solicited or spontaneously reported by the subject. In addition, SAEs and protocol-related nonserious AEs will be collected from the time the subject signs the study-specific informed consent.

drug abuse.

AbbVie will be responsible for Suspected Unexpected Serious Adverse Reactions (SUSAR) reporting for the Investigational Medicinal Product (IMP) in accordance with global and local requirements.

Adverse events will be monitored throughout the study to identify any of special interest that may indicate a trend or risk to subjects.

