## 4 SAFETY MANUAL

## 4.1 Methods and Timing of Safety Assessment

All serious adverse events (SAEs) as well as protocol-related nonserious AEs (e.g., occurrence during Screening) will be collected from the time the subject signed the study-specific informed consent until study drug administration. From the time of study drug administration until 30 days after discontinuation of study treatment, all AEs and SAEs will be collected whether solicited or spontaneously reported by the subject. After 30 days following completion of study treatment and throughout the Post-Treatment Period, all spontaneously reported SAEs will be collected (nonserious AEs will not be collected).

Adverse events of special interest, such as elevated liver transaminases, decreased BMD/ bone fractures, and all mood- and depression-related events, will require additional information, to be collected in the EDC system.

Adverse event information will be collected as shown in Figure 2.

SAEs and Protocol-Related SAEs and Nonserious AEs Nonserious AEs Elicited and/or Spontaneously Reported

Consent Study Drug Study Drug 30 Days After Signed Start Stopped Study Drug Stopped

Figure 2. Adverse Event Collection

AE = adverse event; SAE = serious adverse event

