# 4.2 Recording Data and Analyses of Safety Findings

Adverse events will be coded using the Medical Dictionary for Regulatory Activities (MedDRA). The number and percentage of subjects with treatment-emergent AEs (i.e., any event that begins or worsens in severity after initiation of study drug through 30 days post-study drug dosing) will be tabulated by primary MedDRA System Organ Class (SOC) and preferred term (PT) and compared between arms using Fisher's exact test. The tabulation of the number of subjects with treatment-emergent AEs by severity grade and relationship to study drug also will be provided. Subjects reporting more than 1 AE for a given

MedDRA preferred term will be counted only once for that term using the most severe grade according to the severity grade table and the most related according to the relationship to study drug tables. Subjects reporting more than 1 type of event within an SOC will be counted only once for that SOC.

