2.2 Study Design Overview

This is a Phase 2, randomized, double-blind (sponsor-unblinded), 6-month, placebo controlled, parallel group, multicenter study designed to assess the PK and PD of elagolix and to demonstrate the safety and efficacy of elagolix in women with PCOS.

The duration of the study could be up to 42 weeks, which includes an 8-week Washout (if necessary), a 6-week Screening Period, a 24-week Treatment Period, and a 30-day Post-Treatment Follow-up Period.

The schematic of the study is presented in Figure 1.

Figure 1. Study Schematic

BID = twice daily; M = month; PTFU = post-treatment follow-up; QD = once daily

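### The SAP's treatment-emergent window has no end, whereas the Operations Manual ends it 30 days after dosing; the two can classify serious events differently in women who stop drug early but stay in follow-up

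*SAP*

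**What the plan says.** SAP 9.2.1 gives the definition used for the safety tables: "Treatment-emergent AEs are defined as any AE with the onset that is after the first dose of study drug". Its next sentence brings in events that start on the first dosing day. Neither sentence sets an end. SAP 9.2.2 to 9.2.4 apply the definition to the overview, the SOC and preferred-term tables, and the tables of serious events, discontinuations and deaths, and they add no limit.

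Operations Manual 4.2, which belongs to the protocol as Appendix F, defines the same term as "any event that begins or worsens in severity after initiation of study drug through 30 days post-study drug dosing".

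Three further rules decide whether the difference can show in the data:

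- Collection of all events (Protocol 6.1): "All AEs reported from the time of study drug administration until 30 days after discontinuation of study drug administration will be collected".
- Collection after that (Operations Manual 4.1): "After 30 days following completion of study treatment and throughout the Post-Treatment Period, all spontaneously reported SAEs will be collected". The same sentence says that nonserious events are not collected in that time.
- Follow-up after stopping drug (Protocol 5.6): "subjects who prematurely discontinue study drug treatment should continue to be followed for all regularly scheduled visits", unless consent is withdrawn.

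The planned schedule is "a 24-week Treatment Period, and a 30-day Post-Treatment Follow-up Period" (SAP 2.2).

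**The concern.** One safety category has two governing definitions. They differ only for events that start more than 30 days after the last dose, and the natural answer is that no such events are collected. That answer covers nonserious events under Operations Manual 4.1, but not serious ones. A woman who stops drug early and keeps attending is seen for months off drug, and the Activity Schedule has an adverse event assessment at each clinic visit. A serious event in that time can reach the database, and the SAP would then tabulate it under her dose group as treatment-emergent.

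At stake are the treatment-emergent serious event table and the table of treatment-emergent events leading to death, in arms small enough that one event is visible. If early stopping differs between dose groups, so does the extra time at risk. No efficacy analysis is touched.

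**Working it through.** **Inputs.** Treatment Period 24 weeks = 168 days, and post-treatment follow-up 30 days (SAP 2.2). Window limit 30 days after dosing (Operations Manual 4.2). Planned arms of 20 per elagolix group and 30 on placebo (SAP 2.3).

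**Reproducing the stated duration.** 8 + 6 + 24 + 30/7 = 42.3 weeks, against the stated 42. The period lengths are consistent.

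**Side by side.**

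| | SAP 9.2.1 | Operations Manual 4.2 |
|---|---|---|
| Start | Onset on or after the day of first dose | After start of study drug |
| Worsening | Not mentioned | Included |
| End | None | 30 days after dosing |

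The difference on worsening has little effect, because Protocol 6.1 gives a worsened event its own record: "Worsening in severity of a reported AE should be reported as a new AE". The end of the window is the difference that matters.

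**Extra time that counts only under the SAP.** Extra days = (end of scheduled follow-up) − (day of last dose) − 30, with a floor of 0. The lower figure ends follow-up at Week 24 (day 168). The upper figure adds a 30-day visit after Week 24 (day 198). The upper figure is an assumption, because the documents do not say when that visit falls for women who stopped early and stayed.

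| Last dose | Extra days to Week 24 | With a further 30 days |
|---|---|---|
| Day 1 | 168 − 1 − 30 = 137 | 167 |
| End of Week 1 (day 7) | 168 − 7 − 30 = 131 | 161 |
| Week 4 (day 28) | 168 − 28 − 30 = 110 | 140 |
| Week 8 (day 56) | 82 | 112 |
| Week 12 (day 84) | 54 | 84 |
| Week 16 (day 112) | 26 | 56 |
| Week 20 (day 140) | 0 | 28 |
| Week 24 (completer) | 0 | 198 − 168 − 30 = 0 |

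For a last dose at the end of Week 1, 131/7 = 18.7, about 19 weeks.

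**Example.** A woman takes her last dose at Week 4 and has a serious event at Week 20. She is 140 − 28 = 112 days (16 weeks) off drug, which is 82 days past the manual's limit. The event is treatment-emergent under the SAP and not under the manual.

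**Weight of one event.** 1/20 = 5.0 percentage points in an active arm; 1/30 = 3.3 in placebo. This is the weight of any single event in these arms, not a forecast of how many there will be.

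**The case against.** The strongest case on the other side is that the reach is narrow and the data rules are less clear than they look.

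- A difference needs three things together: early stopping, continued follow-up, and a serious event that starts more than 30 days off drug. For completers the extra time over scheduled follow-up is zero. This stands. The tables can differ; nothing in the documents shows that they will.
- The late-collection sentence in Operations Manual 4.1 covers only spontaneous reports after completion of treatment and does not name early stoppers. The timeline in Figure 2 of that section stops at 30 days, and Protocol 6.1 states no separate later rule for serious events. This stands as an ambiguity. It does not remove the conflict: the sentence expressly continues collection of serious events, and Protocol 5.6 keeps these women in visits where events are assessed.
- An open window over-includes; it hides nothing. All deaths already have their own overview row in SAP 9.2.2, and SAP 9.2.4 lists treatment-emergent serious events by subject. This also stands, and it limits the harm to misclassification.

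Two stronger readings are tempting. A reader might infer that any serious event reported late is counted. The documents do not support that: both definitions turn on when the event begins, so one reported late but starting within 30 days is treatment-emergent under both. A reader might also infer that the ratio of serious to all events is distorted because only serious events enter after day 30. The documents give no basis for a size. It is not even certain that late nonserious events stay out, since retained women still have event assessments and Operations Manual 3.13 records clinically significant examination findings after the first dose as adverse events without an end date.

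**Conclusion.** The SAP rule is wrong as written, because it conflicts with the protocol's own definition in Operations Manual 4.2. The consequence is limited to events that start more than 30 days after the last dose, which over scheduled follow-up means women who stop early and remain in the study. For them the extra counted time to Week 24 runs from 0 days (last dose at Week 20) to about 19 weeks (last dose at the end of Week 1). Each such serious event adds 5 percentage points in an active arm or 3.3 in placebo at the planned sizes.

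This rests on two assumptions: that serious events in retained early stoppers are collected under Operations Manual 4.1, and that these women attend to Week 24. The expected number of affected events cannot be given. This is a minor consistency point that is easy to settle; the primary and key secondary analyses do not depend on it.

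**What to change.** In SAP 9.2.1, replace the open-ended definition with the window of Operations Manual 4.2: onset or worsening from the first dose through 30 days after the last dose. Keep the rule that same-day onset counts. Add one listing of serious events and deaths with later onset, labelled post-treatment, with dose group and days since last dose, so that nothing collected is lost. Keep the existing row for all deaths in SAP 9.2.2.

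The cost is one sentence and one added listing, with no new data collection. Make the change in writing before database lock. The sponsor is unblinded throughout (Protocol 7.1), so the window should not be left to be settled at programming.
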